#### 2.4 Sampling for Qualitative Research

Sampling for qualitative inquiries will be guided by principle of saturation where we will keep interviewing different respondents from varied contexts and backgrounds until the information on themes of interests is repetitive and does not provide more or useful insights. The mix of

respondents and exact questions to ask them is driven by research objectives but the tools, their flow are not standardized. At this stage we anticipate the following.

For qualitative research, in-depth interviews are best suited. Total IDIs of approximately 40 will be distributed across the three states (UP, Rajasthan and Delhi). We currently anticipate 4-6 IDIs with Triggerise managerial and programme staff, 10-12 IDIs with Tiko Pro agents/peers/mobilisers; 10-12 IDIs for mobile health workers, private sector clinics, pharmacists, Kirana stores, Salons, etc; and 12-14 IDIs for users and non-users (beneficiaries). These IDIs will be divided in 2-3 phases so that the initial phases helps in better understanding and design of questionnaires, second phase helps in actual assessment and third phase (if needed) to explain the findings of the quantitative research.

#### 2.5 Questionnaires and Tools

The DRAFT questionnaires and discussion guides (in English) (*Annexures 5 and 6*) and Consent form in both English and Hindi are attached separately (*Annexure 7 and 8*) as follows:

- Tiko enrolled users (in-person surveys)
- Tiko enrolled persons (both users and non-users) (phone surveys)
- Tiko Pro and Agent, Tiko service providers (pharmacists, doctors etc) and shops (IDI guide)

#### 2.6 Quantitative Data Quality Assurance, Processing and Analysis

We would conduct 20% centralised back-checks over phone to ensure in-person visits actually happened and cross-check factual data. For phone surveys, 20% audio- listening-in checks by the coordinator/monitor will be done to cross-verify the factual data. Apart from this, thorough back-office data quality checks (outliers, straight line responses, etc) will be done on pre-identified important variables. A researcher will ensure accuracy of data every third day of the survey by using high-frequency data quality checks for quantitative surveys.

Quantitative data will be entered in a CAPI App on ODK system, transmitted to secure server with 16-key encryption, and downloaded to a dedicated desktop for data. The data will be deidentified immediately first. Second, the processing will include giving variable and value labels, removing duplicate submissions if any, coding open ended responses if they exceed 5% of any categorical question's answers, etc. Then, this de-identified and processed data is submitted to researchers for further analysis in STATA format.

We mainly anticipate descriptive analysis to tabulate indicators related to knowledge, practices, barriers, enablers w.r.t. SRH and MCH services, exposure and use of Tiko platform, how it has helped or not helped or affected their well-being, suggestions and preferences for different components of the platform, etc. We anticipate cross tabulation by socio-economic characteristics, regions (say by Cities), and duration of use.

While no analytical tests are anticipated at this time, we expect to conduct standard bivariate tests (t-test and chi2 test) and regression analysis for more nuanced group mean tests or multiple comparison tests (logit, OLS, mixed models). We will be adjusting for

standard errors for robust inference. In case of statistical inference, we expect one side test with alpha < 0.1 to consider a relationship or test statistic significant.

For cost effectiveness analysis, we will use existing (and publicly available) models such as LIST 2 and Impact. These models will need as inputs data on type and number of contraceptives and family planning services, and number of women who have completed ANC protocol of at least 4 visits. The rest of the inputs and data is in-built in the model to estimate Couple of Years of Protection (CYP) and DALYs. The data needed is available as App backend data without any identifiable information of the respondents such as address, name, phone number. The researchers will only know about the city and age of the beneficiaries along with details of each transaction on Tiko platform – which service pr product, from which service provider, date, and quantum of purchase if any.

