## 2 Research Methods

### 2.1 Overview of methods

This evaluation will be a mixed methods observational design with mainly descriptive and exploratory analysis. The desk research will review documents, secondary data public available (such as NFHS), and any App background data (deidentified) to better understand the programme.

This is followed by qualitative surveys for which 40 in-depth interviews of various beneficiaries and programme stakeholders (demand creators, service providers, lifestyle partners) will be conducted in person or over phone.

Depending on the insights, we will develop a structured quantitative questionnaire and administer the in-person survey to approx. 480 beneficiaries of SRH and MCH services (total). These surveys will seek information on knowledge, practices, barriers, enablers for SRH and MCH services, exposure o Tiko platform, and how it helped or did not help. The survey participants will be women (18-35years of age) who had subscribed to Tiko card between 2018 and 2020. A subset of these would be regular users, a subset will be sporadic

or one-time user and remaining will be 'non-users'. The sample will try to get adequate representation from all categories.

The in-person surveys will be followed with shorter (10-15 minutes) phone surveys with 1200 active users and 600 non-users who had enrolled on Tiko platform. Phone surveys will collect only basic information needed to confirm findings from in-person and qualitative surveys.

The analysis will triangulate the insights from both qualitative and quantitative analysis. We mainly anticipate descriptive analysis to tabulate indicators related to knowledge, practices, barriers, enablers w.r.t. SRH and MCH services, exposure and use of Tiko platform, how it has helped or not helped or affected their well being, suggestions and preferences for different components of the platform, etc. We anticipate cross tabulation by socio-economic characteristics, regions (say by Cities), and duration of use.

While no analytical tests are anticipated at this time, we expect to conduct standard bivariate tests (t-test and chi2 test) and regression analysis for more nuanced group mean tests or multiple comparison tests (logit, OLS, mixed models). We will be adjusting for standard errors for robust inference. In case of statistical inference, we expect one side test with alpha < 0.1 to consider a relationship or test statistic significant.

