#### 2.2 Sample Design and Power Calculations

For detailed 45-50 minutes in-person surveys, 570 respondents will be interviewed across Rajasthan, Uttar Pradesh and Delhi, of which we expect to complete 480 interviews. This sample size was determined on basis of measuring a proportion of 50% with 5 pp error rate and 95% confidence which yields n of 384 and this n was increased by design effect of 1.25 to account for clustering if any at the city level. In person surveys will be done in Agra, Jaipur

For phone surveys, we designed a sample of 2000 complete surveys. Moreover, over sampling will be done in Rajasthan, Uttar Pradesh and Delhi to ensure at least 50 interviews in each city. This sample is designed such that we can conduct descriptive analysis for 3-4 sub-groups (say by cities or by socio-economic categories) with at least 300-400 sample in

each sub-group. The purpose of phone surveys will be to add more statistical power to limited in-person sample size we have for few key questions of interest.

We also expect that the phone surveys and in-person data will be used for statistical group mean tests between regular users and one-time or non-users to compare SRH and ANC related practices between the two groups. It is not a controlled trial of Tiko platform but will be exploratory to understand additionality in service usage of regular users if any.

Assuming at least 150 regular and 150 non-users included in the in-person surveys, the sample will have power to detect 25% relative change or 0.25 SD change from an outcome distributed binomially with mean of 0.50 or with standardized normal distribution with mean 0 and SD of 1 N $^{\circ}(0,1)$  with power of 80% and Type I error of 0.10 with one sided test.

Assuming 500 regular and 500 non-users included in the in-person surveys, the sample will have power to detect 15% relative change or 0.15 SD change from an outcome distributed binomially with mean of 0.50 or with standardized normal distribution with mean 0 and SD of 1 N~(0,1) with power of 80% and Type I error of 0.10 with one sided test.

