#### 2.3 Sampling for In-Person and Phone-Surveys

The sample frame for both surveys will be the Tiko beneficiary database available with Triggerise. Below is the summary of viable database sample frame (exclude smaller sites where the programme is too small to be considered in this study)

Stata	City	Area	Number of		
Sidle			Enrollments	Actual Users	Non-Users
Uttar Pradesh	Agra	Both	34,726	21,743	12,983
Rajasthan	Jaipur	Both	29,588	28,531	1,057
Rajasthan	Ajmer	Urban	7,325	4,532	2,793
Rajasthan	Tonk	Peri Urban	5,176	3,993	1,183
Delhi	Delhi	Urban	3,846	3,142	704
Uttar Pradesh	Firozabad	Peri Urban	1,044	119	925
TOTAL			81,705	62,060	19,645

The following steps will be followed for sampling of in-person survey respondents:

- 1. Restrict the study to only Jaipur and Agra which constitutes 70% of the enrollments and 84% of the actual user base.
- 2. Stratify sample as 150 non-users (enrollment minus users) and 350 users
- 3. Distribute sample in approx. proportion to the actual numbers in both cities for users and non-users as below.

City	Non-users	Actual Users	Total
Agra	100	150	250
Jaipur	50	200	250
Total	150	350	500

- 4. Distribute the sample across the 'Tiko Pro Agents' working in the city. We currently don't have this data, but we expect to complete at least 5 interviews per agent and spread the sample to cover about 25% of the agents working in the city.
- 5. Based on above, randomly sample the Pro Agents from database that will be made available by Triggerise.
- 6. Obtain a list of randomly sampled Beneficiaries from Triggerise for each sampled pro agent. We will obtain 3-times the number of completed interviews required per agent because our scoping visit suggests expecting 30-40% response rate in finding the beneficiary house with help of agent and then getting their consent for the interview. If required, Triggerise will make available more beneficiaries (their name and phone numbers per agent) if the sample size is not achieved.
- 7. NEERMAN enumerators will call each beneficiary sequentially in the list and fix appointments for the in-person interview. The phone records will track validity of numbers, refusals, and consents. Pro agent's help will be sought to find address or in field logistics or to establish our enumerators' bona fides.

The following steps will be followed for sampling of phone-survey respondents:

- 1. Exclude Firozabad which has no programme in 2020

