- 2. Stratify sample as 500 non-users (enrollment minus users) and 1500 users
- 3. Distribute sample in proportion to the actual numbers as below.

City	Non-users	Actual Users	Total
Agra	347	527	873
Jaipur	28	691	719
Ajmer	75	110	184
Tonk	32	97	128
Delhi	19	76	95
Total	500	1500	2000

- 4. Obtain a list of randomly sampled Beneficiaries as above. We will obtain 10-times the number of completed interviews required per agent because our scoping visit suggests to expect 10-15% response rate in phone surveys. If required, Triggerise will make available more beneficiaries (their name and phone numbers per agent) if the sample size is not achieved.
- 5. NEERMAN enumerators will call each beneficiary sequentially in the list and fix appointments for the phone interview. The phone records will track validity of numbers, refusals and consents. Pro agent's help will be sought to establish our enumerators' bona fides if needed.

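### Users and non-users are sampled with different city mixes, yet the bivariate tests listed for comparing them ignore city and the only adjustment stated is to standard errors

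*Protocol*

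**What the plan says.** Section 2.2 expects the data of both surveys, phone and in-person, to serve for a group comparison; its words are "used for statistical group mean tests between regular users and one-time or non-users to compare SRH and ANC related practices between the two groups". The status is set plainly: "It is not a controlled trial of Tiko platform but will be exploratory to understand additionality in service usage of regular users if any". Two power statements follow. One begins "Assuming at least 150 regular and 150 non-users included in the in-person surveys", the other "Assuming 500 regular and 500 non-users included in the in-person surveys".

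Section 2.3 draws users and non-users as separate strata and spreads each over cities. For the in-person survey the rule is "Distribute sample in approx. proportion to the actual numbers in both cities for users and non-users as below"; for the phone survey, "Distribute sample in proportion to the actual numbers as below".

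Sections 2.1 and 2.6 say the analysis is mainly descriptive. Where inference is made, they list "standard bivariate tests (t-test and chi2 test) and regression analysis for more nuanced group mean tests or multiple comparison tests (logit, OLS, mixed models", one-sided at 0.10. No model terms are named. On adjustment they say only: "We will be adjusting for standard errors for robust inference".

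City appears in several other places: as a cross-tabulation variable (2.1, 2.6), as the level of the 1.25 design effect, as an example of a phone sub-group, and as the unit of a minimum interview count (all 2.2).

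**The concern.** The user contrast is meant to throw light on additionality, which bears on the first research question in section 1.3: whether uptake happens because of the platform or regardless of it. Jaipur supplies nearly half of the phone users and almost none of the phone non-users; Agra is the reverse. A crude user vs non-user comparison is therefore partly a Jaipur vs Agra comparison. If practice differs between cities for reasons unrelated to the platform, a t or chi2 test can show additionality that is not there or hide additionality that is. Robust or clustered standard errors change the stated uncertainty. They do not move the estimate, so they leave this bias in place.

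**Working it through.** **Inputs.** Frame and allocation tables in section 2.3; one-sided alpha 0.10 (z = 1.2816) in 2.6; group sizes and effect sizes in 2.2. Binary outcomes are taken near 0.50, as in 2.2. Design effects are ignored throughout.

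**The plan's power figures.** Power = 1 − Φ(1.2816 − d/√(2/n)).
- 150 vs 150, d = 0.25: 0.25/0.1155 = 2.165, power 81% (stated 80%).
- 500 vs 500, d = 0.15: 0.15/0.0632 = 2.372, power 86% (stated 80%).

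Both statements hold with unadjusted two-group formulas. Section 2.2 labels the 500 vs 500 case in-person, but only the phone table has 500 non-users, so it is applied to the phone sample here.

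**City mix.**
- Frame without Firozabad: Jaipur has 28,531/61,941 = 46.1% of users and 1,057/18,720 = 5.6% of non-users.
- Phone sample (columns add to 1,501 and 501 after rounding): 691/1,501 = 46.0% and 28/501 = 5.6%. Difference c = 0.404.
- Frame, Agra and Jaipur only: 28,531/50,274 = 56.8% and 1,057/14,040 = 7.5%.
- In-person sample: 200/350 = 57.1% and 50/150 = 33.3%. Difference c = 0.238. Strict proportionality would put about 11 of the 150 non-users in Jaipur, so the 100/50 split already softens the frame imbalance.

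**Bias of a crude test.** Assume that practice in Jaipur differs from all other cities by a gap g, that the other cities are equal, that regular and one-time users have the all-user city mix, and that there is no within-city effect. The spurious difference is c × g. The rejection rate is 1 − Φ(1.2816 − c·g/SE), with SE = √(0.25(1/n1 + 1/n2)).

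| Comparison | SE | g = 0 | +5 | +10 | +15 |
|---|---|---|---|---|---|
| Phone, 500 regular vs 501 non-users | 0.0316 | 10% | 26% | 50% | 74% |
| In person, 150 vs 150 | 0.0577 | 10% | 14% | 19% | 25% |

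Example, phone at +10: 0.0404/0.0316 = 1.28, so the rate is 1 − Φ(0.00) = 50%.

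**One-time users pooled with non-users.** If a share f of users is one-time, the comparator is non-users plus f × users, with all sampled users included. At +10 and f = 10%, 20%, 33%, 50%:
- Phone: c = 0.311, 0.253, 0.202, 0.162; rates 51%, 43%, 35%, 28%.
- In person: c = 0.193, 0.162, 0.134, 0.110; rates 19%, 18%, 16%, 15%.

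**Opposite sign, g = −10.** Phone power for 7.5 points (0.15 SD) at 500 vs 501: (0.075 − 0.0404)/0.0316 = 1.09, so power falls from 86% to 43%. In-person power for 12.5 points (0.25 SD) at 150 vs 150 falls from 81% to 68%.

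**Sensitivity to the mix of regular users.** If Jaipur's share of the 500 regular phone users were 20%, 30% or 60%, then c = share − 0.056 and the rate at +10 would be about 20%, 31% or 67%.

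**Cost of adjusting for city.** With city fixed effects, SE = √(0.25/Σw), where w = n1·n2/(n1 + n2) within each city.
- Phone, 500 vs 501: w is about 117 Agra, 25 Jaipur, 25 Ajmer, 16 Tonk, 11 Delhi; Σw = 193.1 against 500 × 501/1,001 = 250.2 unadjusted. SE goes from 0.0316 to 0.0360 (+14%). Weights: Agra 117/193 = 60%, Jaipur 25/193 = 13%.
- Phone, 1,501 vs 501: Σw = 320.0 against 375.6; SE from 0.0258 to 0.0280 (+8%).
- Phone, one-third of users one-time and pooled with non-users: SE +3%.
- In person, 150 vs 150: w = 39.1 Agra and 31.6 Jaipur; Σw = 70.7 against 75; SE +3%.

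**The case against.** The strongest reply is that the protocol does not commit to the crude test. It offers regression for the finer group mean tests, which is its own term for the user contrast. A mixed model needs a grouping factor, and the one clustering level named in section 2.2 is city. Covariate lists are commonly left to a statistical analysis plan, which is not shown here. This stands against two stronger readings that a reader might infer. One is that the regression excludes city: the text names model types and no terms, so silence is not exclusion. The other is that city enters only as a cross-tabulation variable: it also sets the design effect and the sub-groups in section 2.2. A design effect, however, allows for variance and does not correct bias.

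The reply does not clear the bivariate tests. They are named for inference, cannot carry city, and nothing says that they are secondary to the regression.

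It is also fair that the in-person imbalance is moderate, that the work is exploratory, and that any figure for the bias is assumed. A reader might further infer that the allocation is faulty or that the additionality result is already known to be biased. Neither follows. The allocation follows the frame (softened in person), and without a city gap in practice the crude test is unbiased. Self-selection into use within a city will remain after adjustment, but that is no reason to leave in a measured imbalance.

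**Conclusion.** The concern holds in a limited form. The city imbalance is a fact of the allocation tables, large by phone and moderate in person. The t and chi2 tests listed for the user contrast would carry any city difference in practice into it, and the stated adjustment would not remove that. Whether the listed regressions would do so cannot be told from the protocol.

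The size is conditional on a city gap that the documents do not give. At an assumed +10 points for Jaipur, the nominal 10% error rate becomes about 50% by phone against non-users alone, 28% to 51% with one-time users in the comparator, and 19% in person. These figures also assume that regular and one-time users share the all-user city mix. The point is worth fixing because the remedy is cheap, but the contrast is exploratory and only one strand of the evidence on additionality.

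**What to change.** In sections 2.2 and 2.6, state that:
- inference on every regular vs one-time or non-user comparison uses a city-stratified test (Mantel-Haenszel) or OLS/logit with city fixed effects;
- crude t and chi2 results are shown beside it as descriptive;
- city-specific estimates are reported with the adjusted estimate;
- self-selection into use within a city remains, so the adjusted contrast is not causal.

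No change to the allocation is needed. City is a sampling variable, so it is already held for every respondent and no interviews are added.

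The cost is some precision. For 0.15 SD, phone power goes from 86% to 79% at 500 vs 501 and from 95% to 92% with all users. For 0.25 SD, in-person power goes from 81% to 79% at 150 vs 150. The second cost is interpretive. With only 28 Jaipur non-users by phone, the adjusted estimate at 500 vs 501 gives Agra about 60% of the weight and Jaipur about 13%, although Jaipur holds 46% of users. If the contrast varies by city, the adjusted figure is largely an Agra result, and this is why the city-specific estimates should stand beside it. The Jaipur phone estimate itself will be imprecise.

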#### 2.7 Qualitative Analysis

We will not be doing typical transcription, translation and coding practice because our researchers will be conducting IDIs themselves and not commercial moderators. After each IDI, a 2-3 page case narrative will be prepared which will organize key discussion points, answers, quotes by 8-12 themes. The themes will be developed by the qualitative lead ([name]). Qualitative lead along with RAs will review all case narratives, identify patterns, contrasts, stories, etc to answer evaluation questions.

#### 2.8 Report and Publication

The TL, RA for quantitative analyses, Qualitative lead ([name]) and RAs for qualitative research will collectively hold a workshop to review both quantitative and qualitative findings and triangulate the insights for the final report. The final report will be developed in a format of a journal publication with <8000 words. The annexures and supplementary material will provide tools, details of analysis, data summary etc. We will also develop a slide deck based on final findings for Triggerise management.

We expect few Triggerise staff to collaborate with us in writing the manuscripts. Their role will be clearly reported as 'funders role' in the manuscript.

## 3 Ethics and Protection of Research Participants

This research is socio-economic-health impact assessment of a private mHealth platform. There is no drug, intervention or device being tested. The platform simply connects users to service providers and products available as per existing government rules and approvals already. So, it is basically a study of how a 'market place' actually helps beneficiaries?

Overall, the research should merit expedited IRB review. However, below is our assessment of risks and benefits to the participants.

**Interview of Tiko Users** – the platform users' age ranges from 18 years to 45 years. The qualitative IDIs or field visits include discussion with a few users about the practices, knowledge, benefits, barriers or contexts of users interviews. However, the quantitative surveys will be conducted of similar Tiko platform users. For all the respondents written consent will be administered and recorded.

**Uneasy questions** – Some of the questions related to contraceptives, pregnancy, family planning can be perceived as private. The respondent has a right to refuse answer to such and any questions. The interviews are also conducted by female interviewers in privacy. The consent form will specifically mention this risk and their right to refuse.

**Data privacy and security** – Qualitative interviews will be audio recorded along with notes, quantitative interviews will be conducted using CAPI/CATI apps, and both interviews will collect identifiable information such as name and phone number for survey management purposes only. These variables will be used in case of repeat visits and back checks of data only. We will also collect GPS coordinates purely to track movement of enumerators in field surveys but this data will not be linked to individual respondents.

Qualitative interviews/discussions will record name and phone numbers only in a diary and use a pseudo name (Rafiki, Doc, Bhai, etc) and never real name in the conversation once the audio recording starts. The case narrative for each interview will be written up within 3 days of the interview. After study conclusion all audio files will be deleted after 3 months period along with diaries which can link audio recordings to specific respondents. All this data will be controlled by a single person on non-networked computer.

Quantitative data with CAPI/CATI will only display name to the interviewer but the raw data will automatically deidentify/mask any identifiable data before it is shared with researchers for analysis. Only a single data manager will be responsible to keep survey data and linked identities of respondent (name and phone number) as two separate files in a non-networked computer under password protection. This data will be deleted three months after study completion. The data transmission between devices and data security on CAPI server follow 16-key encryption and comply with IT Act of India 2012.

**COVID-19 Related Infections** – The risk is a possibility during in-person interactions but we will adhere to ICMR guidelines on minimizing this risk such as use of a mask, sanitization of hands and tablets before/after interview, and maintaining a distance of 4-6 feet during interviews. Every enumerator will be given a covid-19 test 2-3 days prior to start of field work begins. Everyday morning and evening oximeter and temperature checks for enumerators will be done. Respondents will not be interviewed if they report flue like symptoms or report having COVID-19 in 2 weeks preceding the survey.

**Benefits of participation:** There will not be any monetary benefits to the survey participants, but they will be told that their participation helps in greater social good of improving the platform, scaling it up and sustaining it which can benefit others like them. However, we seek IRB permissions to in-kind care package for phone survey participants to ensure higher response rate. We are planning to offer a care package in form of Tiko miles (equivalent of money they can spend with linked service providers) or phone recharge coupon, etc.

**Consent Administration:** The consent form for quantitative and qualitative survey respondents are attached as **Annexure 7 and 8**. These consent forms clearly discuss survey purpose and methods, above risks and benefits, rights of respondents, and contact information of the IRB and ethics officer at NEERMAN who can be contacted in case of

grievances. We will record the consent in the tablet or on printed consent form with their (digital or actual) signature along with enumerator as a witness. In case a respondent refuses to sign the consent, then we will administer a verbal consent only but audio record it and get signature of a third party witness.

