#### 1.2 Research objective

Triggerise has commissioned an independent impact assessment of the platform to understand what values and benefits are derived at the end user level – both health impacts at the beneficiary level and economic impact at the 'agent' level who is responsible to onboard the beneficiary on the platform and link them with services. The study also aims to gain insights on the merits of the various platform features and their efficacy. Triggerise expects the research organization to publish the findings of the study in an international journal.

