#### 1. Health Impact and users perception

- Do users take up SRH and maternal health products and services because of our innovation or regardless of it? (In other words, are we stimulating new SRH users or are the members previously active SHR clients?)
- When they first enrolled in the program, were they using contraceptives or are their first-time users? Did the platform make it easier for them? How? What other benefit appeal? If they were switchers, what were the motivators to switch from their previous source of health services to ours?
- How often did they use the platform? If they were repeat users, what was their motivation to come back to the platform? If they were only one time users, why did they not come back?
- Does the Tiko digital platform increase consistent use of short-term contraceptive methods? Why or why not?
- Does the Tiko digital platform increase consistent MNCH behaviours? Why or why not?
- What did they like about the platform and the experience? What barriers did it solve for them? Will they use it again? Will they recommend their friends to use?
- Why did they choose Tiko platform? What would they have done if it were not available as an option?
- What perception or behaviour shifts have our intervention been able to address around stigma, access, privacy, dignity/respect, willingness to pay, etc?

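### The statement of benefits tells participants, before they answer, that taking part helps to expand and sustain the platform whose value the survey is meant to assess

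*Protocol*

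**What the plan says.** Protocol section 3 (Benefits of participation) offers no monetary benefit to survey participants. Instead "they will be told that their participation helps in greater social good of improving the platform, scaling it up and sustaining it", with the further remark that others like them can benefit.

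The paragraph on consent administration in the same section covers the forms for quantitative and qualitative respondents (Annexures 7 and 8) and states: "These consent forms clearly discuss survey purpose and methods, above risks and benefits, rights of respondents". Consent is universal: "For all the respondents written consent will be administered and recorded".

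Section 1.2 describes the study as an "independent impact assessment of the platform". Section 2.6 plans to tabulate exposure to the platform and "how it has helped or not helped or affected their well-being". Among the questions in section 1.3 are: "What did they like about the platform and the experience? What barriers did it solve for them? Will they use it again", and whether women would recommend it to friends. Section 2.2 adds "statistical group mean tests between regular users and one-time or non-users to compare SRH and ANC related practices between the two groups".

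**The concern.** A statement of purpose given at consent sets the frame in which the answers are given. This one treats scaling up and sustaining the platform as a social good, and so leans towards one answer to the study's own question. The outcomes most exposed are opinions and intentions that the woman reports herself: perceived help, liking, reuse and recommendation. If the frame lifts these, the descriptive tables are too favourable. Every participant is to be told the same thing, so there would be no unprimed group from which to estimate or remove the effect.

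A second, weaker route leads to the group comparison. Users draw discounts and miles from the platform (section 1.1), so the idea of sustaining it may carry more weight for them than for women who enrolled but never used it. Any such difference in reaction would add to the apparent difference between the groups.

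**Working it through.** **1. Does the message come before the answers?** The benefits paragraph fixes what participants are told. The consent paragraph says the forms discuss the benefits set out above it. Section 3 requires consent from all respondents. Together these place the message ahead of the interview. The annexed forms are not available, so their exact wording cannot be checked.

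**2. Does anything planned counter it?**
- The right to refuse and the use of female interviewers in private (section 3) deal with sensitive questions, not with framing.
- The 20% back-checks and 20% listening-in (section 2.6) verify visits and factual data.
- App backend data are named for the desk review and as input to the cost-effectiveness models (sections 2.1 and 2.6), not as a check on survey answers.

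The protocol states no neutral purpose or other safeguard against favourable reporting.

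**3. The plan's own figures.** Inputs from section 2.2: one-sided alpha 0.10 (z = 1.2816), 80% power, 0.25 SD at 150 v 150, 0.15 SD at 500 v 500. Power = Φ(d/√(2/n) − 1.2816).
- 150 v 150: 0.25/√(2/150) = 0.25/0.1155 = 2.165; Φ(2.165 − 1.2816) = 81.2%.
- 500 v 500: 0.15/√(2/500) = 0.15/0.0632 = 2.372; Φ(2.372 − 1.2816) = 86.2%.

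The binomial versions (0.50 v 0.625 and 0.50 v 0.575) give 81.8% and 86.4%. The stated 80% is met, so sample size is not the problem here.

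**4. Group comparison (illustration).** The documents give no size for the bias. Assume both true rates are 50%, regular users over-report by b more than the comparison group, and the one-sided test looks for higher rates in regular users. The standard error is √(2 × 0.25/n), which is 0.0577 at n = 150 and 0.0316 at n = 500. The chance of a false positive is P(Z > 1.2816 − b/SE).

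| Assumed excess b | 150 v 150 | 500 v 500 |
|---|---|---|
| 0 | 10% | 10% |
| 2 points | 17.5% | 25.8% |
| 3 points | 22.3% | 37.0% |
| 5 points | 33.9% | 61.8% |
| 8 points | 54.1% | 89.4% |

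For b = 5 points: 0.05/0.0577 = 0.866 and P(Z > 0.416) = 0.339; 0.05/0.0316 = 1.581 and P(Z > −0.300) = 0.618. The larger sample makes the error worse, because it shrinks the standard error and leaves the bias as it is.

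**5. Descriptive results (illustration).** Section 2.2 sizes the in-person survey for ±5 points at 95% confidence: 384 × 1.25 = 480. The standard error is then 5/1.96 = 2.55 points. If the frame lifted an item by an assumed 5 points in everyone, the shift would be 1.96 standard errors. The interval would cover the true value with probability Φ(0) − Φ(−3.92), about 50% instead of 95%. Items put to users only have a wider margin and lose somewhat less coverage.

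**The case against.** The strongest reply is that the sentence is milder than it first looks. It names improvement of the platform first, which leaves room for criticism. It ties the good to taking part, not to a favourable answer, and the benefit goes to others, not to the respondent. Section 1.3 also asks why one-time users did not come back. All of this stands and limits the likely size of the effect. It does not make the statement neutral, because scaling up and sustaining the platform are still presented as the good served.

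The reply on the group comparison also stands. Participants in both groups are to be told the same thing, and non-users are themselves enrolled women. The planned contrast concerns reported SRH and ANC practices, which are less open to this framing than opinions are. Any assumed differential inflates a one-sided test, so the table in the working does not show that this sentence produces one.

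A reader might infer that the sentence also selects supporters into the sample, given expected response of 30-40% in person and 10-15% by phone (section 2.3). The documents do not support that. These are ranges for overall response, not rates for favourable and unfavourable women. The in-person range includes failure to find the house, and the call records also track whether numbers are valid. Part of the non-response therefore arises before anyone hears the consent text.

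Finally, the study is declared mainly descriptive and exploratory, and the service and product inputs to the cost-effectiveness models come from App backend data that this wording cannot touch. That narrows the reach of the point but leaves the survey results exposed.

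**Conclusion.** The point holds as a correctable weakness in wording. The protocol commits the study to a platform-favouring statement before self-reported answers about that platform, and no stated check addresses it. The main exposure is the descriptive perception results. The comparison of reported practices is exposed only to the extent that users react more than one-time or non-users.

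The size is unknown. The figures of about 34% (150 v 150) and 62% (500 v 500) rest on an assumed 5-point excess in regular users, true rates of 50% in both groups, and a test looking for higher rates in regular users. They show sensitivity to such a bias, not its likely value. A reader might infer that regular users gain by answering favourably, or that the group comparison is invalid; the documents establish neither.

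**What to change.** In section 3, and in Annexures 7 and 8 if they carry the same text, delete the part about scaling up and sustaining the platform and the benefit to others like the respondent. Replace it with neutral wording that still discloses what is being assessed. For example: *this is an independent assessment of women's experience with the Tiko platform and of their health practices; good and bad experiences are equally useful to us; there are no right or wrong answers; what you answer will not affect your card, discounts or miles.*

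The cost is wording only. Section 2.5 still marks the questionnaires as drafts and section 3 is still seeking IRB permission, so the change can be made before fieldwork. Sample size and analysis are unaffected. The downside is a slightly weaker appeal to take part.
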